Our long-term goal is to understand how PTSD increases risk of CVD morbidity and mortality so that preventative and therapeutic strategies can be developed. Impaired sleep is a hallmark symptom of PTSD (American Psychiatric Association, 2013), with insomnia reported by as many as 90% of patients who have received first-line PTSD treatment (Zayfert & DeViva, 2004; Ohayon & Shapiro, 2000). It is well established that insomnia is associated with increased CVD risk (Bonnet & Arand, 2007), but this association has not been studied in those with PTSD (Sofi et al., 2014). The objective of this application is to establish the contribution of insomnia to the markedly increased atherosclerotic CVD risk among those with PTSD, and to examine whether this risk can be ameliorated.

Based upon recent evidence, including our own preliminary data, our central hypothesis is that insomnia in those with PTSD is a potentially modifiable feature of PTSD that contributes to CVD. Unfortunately, even following intensive evidence-based psychotherapy for PTSD, insomnia typically remains an unresolved problem (Belleville, Guay, & Marchand, 2011). Recent evidence suggests that a behavioral sleep intervention, Cognitive Behavioral Therapy for Insomnia (CBT-I), can increase improve sleep quality and duration, and promote consolidated sleep among individuals with PTSD (Talbor et al., 2014); however, it is currently unknown whether these improvements would have a favorable impact on CVD risk.

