delivered by nonspecialist providers (Buysse, Germain, & Moul, 2011; Manber, Carney, & Edinger, 2012; Neylan, 2011). CBT-I is delivered as a short-term intervention and produces long term gains in sleep (Morin et al., 1999; Murtagh & Greenwood, 1995). CBT-I has been shown to be effective even among individuals with other medical and psychiatric morbidity including cancer, depression, alcohol dependence and chronic pain (Smith, Huang, & Maber, 2005). Theoretically, a behavioral model of sleep is applicable to PTSD in that the traumatic event can serve as an initiating event for insomnia while behavioral factors (e.g., time in bed extension) may lead to chronic insomnia (Spielman, Saskin, & Thorpy, 1987). An 8-week course of CBT-I has recently been shown to improve objective and subjective sleep in individuals with PTSD (Talbot et al., 2004), and gains were maintained at 6-months. Bonnet and Arand (2007) have recommended that future research is needed to determine whether sleep interventions that result in improved sleep are also temporally related to reduced CVD risk.

B.6. Biomarkers of Cardiovascular Risk

The logistical and financial obstacles (e.g., large sample sizes, extended follow-up periods of years) associated with infrequent "hard" clinical endpoints (e.g., myocardial infarction, stroke, death) has proven to be a major challenge to furthering our understanding of the optimal ways to treat vulnerable patients because of the obvious logistical and financial obstacles such investigations present. One solution to this problem is to first study intermediate markers of risk in vulnerable patients to untoward cardiac events (Rozanski, Blumenthal, Davidson, Saab, & Kubzansky, 2005). Examination of changes in intermediate endpoints can provide important insights into the mechanisms and potential value of clinical interventions and has a number of important advantages over "hard endpoints," in that fewer patients are required to detect treatment effects and changes in cardiac risk can be reliably and objectively measured over short follow-up intervals. Following the guidelines advanced by a panel of prominent cardiovascular scientists (Naghavi et al., 2003), we propose to examine intervention effects on biomarkers of atherosclerotic cardiovascular risk (i.e., "intermediate endpoints") in "vulnerable" PTSD patients with insomnia.

B.6.1. Ambulatory Blood Pressure (ABP) and Blunted Nighttime Blood Pressure (BP) Dipping.

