Sleep duration will be defined as TST (calculated by subtracting all periods of wakefulness from the time spent in bed). WASO is calculated by summing wakefulness periods after initial sleep onset and before final awakening. Sleep efficiency is defined as the ratio of total sleep time divided by TIB (TST/TIB). Sleep fragmentation (a secondary outcome) is defined as the sum of percent mobile and percent immobile bouts less than 1-minute duration to the number of immobile bouts for a given interval (Respironics Incorporated, 2008). Actigraphy will be used as the primary source for these variables (Lauderdale, Knutson, Yan, Liu, & Rathouz, 2008). Scoring of actigraphy data will proceed in accordance with the guidelines by the Society of Behavioral Sleep Medicine (Ancoli-Israel et al., 2015). The sleep diary will include queries about removal of the actigraphy watch from the wrist, and unusual activities during the monitoring period (e.g., travel), and these factors will be considered when scoring. The event marker will be used as the primary method for establishing “into bed” and “out of bed” times. However, when study participants fail to press the event marker, (i.e., no marker on actigraphy output), light sensor data and sleep diaries will be combined with accelerometry data to establish “into and out of bed” times.

C.5.2.4. Daily Sleep Diaries. Subjective sleep estimates will be obtained concurrent with actigraphy, using a Qualtrics survey. Participants will record their sleep using the recently developed consensus sleep diary (Carney et al., 2012) to assure comparability across insomnia research studies. Sleep diaries will be used to calculate averages for: TIB, sleep onset latency (SOL) (Marino et al., 2013), TST, WASO, and SE. The sleep diary is considered the gold standard of self-reported sleep (Buysse et al., 2006). We will use Duke Qualtrics to gather the daily sleep diaries.

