C.6.1. Assessment of 24-hour Ambulatory Blood Pressure (ABP). We have experience measuring 24-hour ABP and will use the Oscar 2 ABP monitor (Suntech Medical Inc., Raleigh, NC), which has been validated by previous investigators (Goodwin, Bilous, Winship, Finn, & Jones, 2007; Jones, Bilous, Winship, Finn, & Goodwin, 2004). Clinic BP will be determined according to the new ACC/AHA guidelines (Whelton et al., 2018) with three readings taken after five minutes of quiet rest in a seated posture, each separated by 2 minutes, using the Oscar 2 BP monitor together with appropriate cuff size, and averaged to represent clinic BP. Subsequently, the ABP monitor will be programmed to take BP measurements every 20 minutes throughout the waking hours and every 30 minutes during the nighttime sleep period. We have used this procedure with excellent participant acceptability and compliance in numerous previous studies (Blumenthal, [name], & Gullette, 2000; Carels, [name], Szczepanski, & Blumenthal, 2000; Prather, Blumenthal, Hinderliter, & [name], 2011; [name] et al., 2011; [name], Thurston, Steffen, Blumenthal, Waugh, & Hinderliter, 2001). A successful 24-hour study will require at least 80% of the total readings to be valid, with no more than two consecutive hours lacking a valid reading (White et al., 2006). Unsuccessful ABP studies will be repeated.

In addition to mean 24-hour ABP, mean waking and nighttime ABP will be computed, with the nighttime sleep period defined by self-report and confirmed by actigraphy ([name] et al., 2001; [name] et al., 2011; [name] et al., 2002). Nighttime BP dipping will be defined as the percentage of the decline in nighttime systolic blood pressure (SBP) [(mean daytime SBP- mean nighttime SBP/mean daytime SBP) \times 100]; SBP dipping defined in this way is a continuous variable that will be a primary outcome measure in this proposed RCT. In addition, for descriptive purposes, a SBP dip \geq 10% will be classified as normal “dipper”, while $<10\%$ will be classified as “non-dipper”, with secondary analyses evaluating intervention effects on dipping status. Twenty-four-hour ABP assessments will be obtained at pre-randomization baseline, upon completion of the 8-week intervention, and at 6-month follow-up, in order to evaluate intervention effects on ABP and nighttime BP dipping.

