MLM can accommodate data missing at random, using maximum likelihood-derived estimates based on all available data. That said, data may be missing not at random (MNAR). That is, the outcome data may be systematically missing, for instance, from participants who experience no benefit from CBT-I. Nevertheless, even in the case of MNAR data, estimates derived from analyses examining Hypothesis 2 (addressing the within-person associations of change in insomnia with change in CVD risk) and the Supplemental Aim are unlikely to be affected by data missingness. After all, even if participants who benefit the least from CBT-I drop out of the study, we still anticipate observing the same magnitude of association between improved sleep and changes in cardiovascular biomarkers and QoL. By contrast, Hypothesis 1, which examines clinical response to CBT-I, would be affected by MNAR data. As such, we will conduct sensitivity analysis on three missing data approaches for Aim 1. First, we will conduct a completer analysis, analyzing only data from participants who complete each of the three assessments. Second, we will allow the maximum-likelihood estimation to generate estimates for all available data. In a third approach, we will use an intent-to-treat approach, assuming that missing post-intervention and/or 6-month follow-up data are evidence of stagnation. Specifically, we will use last observation carried forward in the cases of missing data.

D.3. Primary and Secondary Analyses

To examine the degree to which CBT-I is associated with improved sleep efficiency and insomnia severity index score (manipulation check), linear MLM will be used to model sleep outcomes as a function of treatment (CBT-I, control), time (baseline, post-intervention, 6-month follow-up), and the interaction between treatment and time. Planned treatment contrasts in change from baseline to post-intervention and 6-month follow-up will be examined within the context of the model. To determine the degree to which CBT-I is associated with improved CVD risk biomarkers (Hypotheses 1a), each of the 6 CVD risk variables (24-hr SBP, nighttime SBP dipping, FMD, 24-hr epinephrine, and norepinephrine) will also be modeled as a function of treatment, time, and their interaction, with planned treatment contrasts in change from baseline at post-intervention and 6-month follow-up. Dichotomized 10-year ASCVD risk scores (Hypothesis 1b) and QoL scores (Hypothesis 1c) will similarly be modeled via logistic MLM.

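### Nighttime SBP and dipping are averaged over a sleep window that CBT-I can itself change, and no planned analysis separates this from lower pressure during sleep

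*Combined protocol and SAP*

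**What the plan says.** Section C.6.1 sets the night from the recording itself: "mean waking and nighttime ABP will be computed, with the nighttime sleep period defined by self-report and confirmed by actigraphy". Dipping is the percentage fall from the daytime to the nighttime mean SBP, and "SBP dipping defined in this way is a continuous variable that will be a primary outcome measure in this proposed RCT". The recording is repeated: "Twenty-four-hour ABP assessments will be obtained at pre-randomization baseline, upon completion of the 8-week intervention, and at 6-month follow-up". Readings are taken "every 20 minutes throughout the waking hours and every 30 minutes during the nighttime sleep period". No clock window common to the visits is set, and no rule removes readings taken while the participant lies awake within the period.

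On the treatment, the Specific Aims say that CBT-I "can increase improve sleep quality and duration, and promote consolidated sleep among individuals with PTSD", and Hypothesis 1 uses higher sleep efficiency as its manipulation check. Section B.5 says that "behavioral factors (e.g., time in bed extension) may lead to chronic insomnia". The reference cited there is, by its title in the reference list, about restricting time in bed as a treatment.

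Section C.1 lists both nighttime BP and dipping as primary outcomes. Section D.3 names the modelled variables as "24-hr SBP, nighttime SBP dipping, FMD, 24-hr epinephrine, and norepinephrine", which leaves out nighttime SBP. Nothing in D.1 to D.3 deals with a night window that changes between visits.

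**The concern.** A day-to-night contrast measures blood pressure regulation cleanly only if the split between day and night means the same thing before and after treatment. Here the split follows sleep behaviour, which is what CBT-I sets out to change. If a participant spends fewer wakeful hours in bed, fewer waking-level readings enter the night mean. Night SBP falls and dipping rises, although pressure asleep and pressure awake are what they were.

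The reading of a primary outcome is at stake. A positive dipping contrast could reflect lower pressure during sleep, more of the night spent asleep, or a shorter window. The plan has no analysis that tells these apart.

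**Working it through.** **The plan's own figure.** D.4 claims 80% power for d = 0.41 at an effective sample size of 215. With 10% attrition twice, 121.5 people have three visits, 13.5 have two and 15 have one. At an ICC of 0.50 this gives 121.5×3/2 + 13.5×2/1.5 + 15 = 215.25. Split 1:2, power at d = 0.41 is 0.81. The figure reproduces and serves below as a yardstick.

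**Inputs for the example (all assumed; the documents give none).** Waking SBP D = 128, sleeping SBP S = 113, both fixed. Window 8.5 h with 2.0 h awake, then 7.0 h with 0.7 h awake. SBP awake in bed, A, is varied.

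**Formulas.** Night = [(window − wake)×S + wake×A]/window. Dipping = (day − night)/day × 100. The 1.5 h removed from the night joins the day, either at waking pressure (the person gets up and pressure rises) or at A (the hours are only relabelled).

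**Base case, A = 128.**
- Night before: (6.5×113 + 2.0×128)/8.5 = 116.5. After: (6.3×113 + 0.7×128)/7.0 = 114.5.
- Dipping: 8.96% to 10.55%, a gain of 1.59 points.
- Time-weighted 24-h mean: (17.5×128 + 6.5×113)/24 = 123.9, then (17.7×128 + 6.3×113)/24 = 124.1. It does not fall because the example has sleep going from 6.5 to 6.3 h.

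**Varying A.** At A = 120.5 the night goes from 114.76 to 113.75. The baseline day mean is 128. If the removed hours keep their in-bed pressure, the later day mean is (15.5×128 + 1.5×120.5)/17 = 127.34.

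| Awake-in-bed SBP | Gain, removed hours at 128 | Gain, removed hours at A |
|---|---|---|
| 128 | +1.59 | +1.59 |
| 120.5 | +0.79 | +0.33 |
| 118 | +0.53 | −0.09 |
| 116 | +0.32 | −0.42 |

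With sleep held at 6.5 h instead (7.2 h window, 0.7 h awake) and the removed hours at A, the gains are +1.62 at 128, +0.40 at 120.5, 0.0 at 118 and −0.32 at 116.

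**The two routes separated** (a second assumed set: sleeping 112, day 130, A from 118 to 130).
- Consolidation only, 8 h in bed, sleep efficiency 75% to 85%: dipping rises 0.5 to 1.4 points and the time-weighted 24-h mean falls 0.2 to 0.6 mm Hg.
- Shortening only, 6 h asleep, 8 h to 7 h in bed, removed hour kept at A: dipping rises 0.0 to 1.5 points and the 24-h mean does not move.

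**Against the yardstick.** Assume a dipping SD of 5 to 8 points, with every CBT-I participant shifting and no control shifting. Gains of 0.3, 0.8 and 1.6 points are then d = 0.04 to 0.06, 0.10 to 0.16 and 0.20 to 0.32. As shares of 0.41 these are 9% to 15%, 24% to 39% and 49% to 78%.

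**The case against.** Four objections carry weight.

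**Consolidated sleep is the hypothesis.** If more of the night is truly asleep, pressure over those hours is truly lower, and the second set of figures shows the 24-h mean falling with it. That part is a real effect of better sleep. Only the shortening route is pure relabelling, and the documents do not say outright that CBT-I shortens time in bed. That is inferred from B.5 and its cited source.

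**The direction is not fixed.** A reader might infer that the shift always favours CBT-I. It does not: relabelled hours carry their lower pressure into the day mean, and the gain vanishes or reverses once awake-in-bed SBP is about 118 or less. Nor do the documents establish that control windows stay still, since controls continue usual care and are asked about insomnia treatments received.

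**Sleep period may not mean time in bed.** C.6.1 speaks of a sleep period, while the example uses time in bed. If half of the wake time fell before sleep onset or after final awakening and so lay outside the window (assumed), the base case becomes 7.5 h with 1.0 h awake to 6.65 h with 0.35 h awake, and the gain drops from 1.59 to 0.95 points. Actigraphic confirmation could even mean asleep-only scoring, which would hold night SBP fixed. The text states no such rule.

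**Other outcomes give partial cover.** The 24-hr SBP needs no day/night split and is modelled in D.3, alongside FMD and catecholamines. A reader might infer that a positive dipping result would be uninterpretable. That goes too far: those outcomes help, although no stated rule links them to the reading of dipping.

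**Conclusion.** The concern holds in a limited form. The plan lets the treatment alter the window behind a primary outcome, keeps awake readings in it, and plans no check. Dipping can rise with sleeping and waking SBP unchanged. In the assumed example the rise is about 1.6 points at most, 0.3 to 0.8 when awake-in-bed SBP is midway, and about zero or slightly negative at 118 or below if the removed hours keep their pressure. All pressures, sleep times and SDs are assumptions, so the size in this trial is unknown. The direction generally, but not always, favours CBT-I.

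This does not show that a dipping benefit would be an artefact, or that the sleep-period definition is wrong. It shows that the planned analysis cannot say how much of a benefit is lower pressure during sleep. Hypothesis 2 shares the weakness, because its predictor, sleep efficiency, is closely tied to the asleep share of the same window. No figure is put on that here.

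**What to change.** Keep the sleep-period definition as primary, and state whether the period runs from into bed to out of bed or from sleep onset to final awakening. For dipping and for nighttime SBP, which D.3 should name, prespecify before outcomes are examined by arm:

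- **(a)** the same contrasts using only night readings taken during actigraphy-scored sleep;
- **(b)** the same contrasts using each participant's baseline, pre-randomisation clock window at every visit, with day hours fixed likewise. A window built from the hours common to all attended visits would depend on post-randomisation sleep and attendance, so it should not be used.

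Report by arm the sleep-period length and the share of night readings during scored wake. If dipping improves only under the visit-specific window, attribute it to changed sleep timing or consolidation and not to lower pressure during sleep. Do not make the primary test depend on agreement.

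In the base case, (a) gives (128 − 113)/128 = 11.7% at both visits. If the later 7.0 h lies inside the baseline 8.5 h, (b) gives a night of (6.3×113 + 2.2×128)/8.5 = 116.9 and dipping of 8.7%, against 9.0% before. The 1.6-point gain disappears in both.

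The cost is programming and SAP wording, since the ABP recordings and actigraphy are already collected. Analysis (a) has fewer readings and wider intervals. Its day mean still follows the visit, so dipping in (a) can dip slightly if removed hours join the day at lower pressure (11.7% to 11.3% at A = 120.5). Analysis (b) is conservative because hours newly spent out of bed count as night: at A = 120.5, with those hours at 128, dipping goes from 10.3% to 9.2%.

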C.6.3. 24-hour Urinary Catecholamines (Epinephrine and Norepinephrine). Patients will be asked to collect urine over a 24-hour period (Blumenthal, [name], & Gullette, 2000; Hughes, Watkins, Blumenthal, Kuhn, & [name], 2004; [name], Steffen et al., 2002; Zhang et al., 2011, White, Brunner, & Barron, 1995). Urine samples will be kept cold by storage in a portable cooler throughout each 24-hour sample period. Urine will be collected in three containers provided to each participant in a portable cooler, with careful instructions to collect daytime/awake urine in containers labeled accordingly, including the last collection before bedtime; any nighttime/sleep period urine collection will be collected in the container labelled “nighttime”, and participants will be instructed to void using that collection container as soon as they get up in the morning. Samples will be assayed for norepinephrine, epinephrine, and creatinine. Catecholamine levels will be expressed as urine concentration ($\mu\text{g}/\text{ml}$) per urine concentration of creatinine (mg/ml), yielding norepinephrine and epinephrine values of μg per mg creatinine for each sample. This provides catecholamine excretion indices that are corrected for individual differences in body size and urine volume (White, Brunner, & Barron, 1995). In prior studies of circadian changes in sympathetic activity, urinary catecholamine data have proven informative, with low subject burden and excellent compliance (Blumenthal, [name], & Gullette, 2000; Hughes et al., 2004; [name], Steffen et al., 2002; Steffen, Hinderliter, Blumenthal, & [name], 2001). 24-urinary catecholamines (epinephrine and norepinephrine) have also been shown to be inversely related to sleep efficiency measured by actigraphy (Zhang et al., 2011).

C.6.4. ASCVD – 10-Year Consensus Markers. We will collect demographic and clinical information required to characterize study participants' 10-year risk for ASCVD, and calculate it at baseline, post CBT-I, and at 6-month follow-up. The variables that are included in risk assessment equations are age, race, total and HDL-cholesterol, systolic BP (including treated or untreated status), diabetes, and current smoking status. Information on age, gender, race, and treatment of hypertension will be collected. Clinical information will be obtained from medical record review. Lipids and glucose levels will be determined from blood specimens drawn between 8:00-10:00 am following overnight fasting. All blood samples will be kept refrigerated until transfer to the appropriate laboratories. Lipids will be determined by enzymatic methods.

C.7. Risk/Benefit Ratio and Protections Against Risk

C.7.1. Study Risks. In both conditions, with regards to completing study measures, there is a risk of

discomfort or distress in answering questions, especially questions related to traumatic experiences. However, distress and discomfort related to questionnaire completion are usually temporary and well-tolerated. With the blood draw, there is a risk of bruising at the site of the draw and rarely, fainting and/or infection. There is a minimal risk of disrupted sleep associated with the sleep apnea assessment. The Oscar 2 ABPM has built in safe-guards to avoid over-inflation or prolonged inflation of the cuff, as well as a measurement abort key that can be activated by the participant. The FMD assessment will include blood pressure cuff inflation for 5 minutes, which has the risk of causing tingling and discomfort in the arm. There are no known risks associated with use of the actigraphy or the Qualtrics sleep diary. There is a potential risk associated with the loss of confidentiality of study data, although all due precautions will be taken to minimize such risk. Participants are provided information during the informed consent process about risks inherent with mobile app download and use, and use of a Duke-owned, loaned device.

C.7.2. Potential Benefits. While participants may benefit from improved sleep and/or reduced insomnia complaints, there are no guaranteed benefits to the individual participant and no immediate benefits of the proposed research to others. Information gathered from participants may help us to establish a link between sleep impairment and autonomic and inflammatory markers of CVD risk among individuals with PTSD. In our opinion, the anticipated benefits of this study outweigh the potential risks.

C.7.3. Protection from Risk. Participants are informed clearly during the initial informed consent process that the study is completely voluntary, and that they may refuse to answer any items that they do not wish to answer on the questionnaires and interviews. They are also informed that they are free to decline participation in any procedure and can withdraw from the study at any time. Potential risks will be minimized by carefully screening potential participants according to the inclusion/exclusion criteria, closely monitoring symptom levels, and following established laboratory procedures. Patients will complete the MoCA to assess cognitive function. Patients who score <20, which suggests the presence of cognitive impairment, will be informed of the results and encouraged to discuss the findings with their personal care physician for further evaluation and treatment if necessary. With regards to determination of decision making capacity of potential participants, our laboratory has a standard procedure for determining understanding of the study procedures, risks, and benefits. We utilize this procedure if we have any reason to suspect that the participant may have difficulty in the consent process (e.g., traumatic brain injury impacting cognitive function, active psychotic symptoms). In this procedure, the study coordinator providing the informed consent information evaluates understanding of the procedures at several different time points during the process by asking questions like “Do you understand what we’re asking you to do?” and “Do you have any questions about the risks of the study? Can you tell me what you understand the risks to be?”

C.7.4. Data Storage and Security. Data that links participants to information collected in the course of a given study will be kept separately from identifying information in an electronic, password-protected MS Access database stored at duhsnas-pri\dusom_psych\private\irb\[name]\PTSD Insomnia; the key connecting identifying information and data will be stored here as well. Hard copy paper records will be stored in a locked filing cabinet in the study coordinator’s locked office within [name]

laboratory space at Duke University Medical Center. Information from the interview and/or questionnaires may be entered into a computerized database that will be stored on the DUMC server at duhsnas-pri\dusom_psych\private\irb\[name]\PTSD Insomnia in a password-protected database. This database is accessible only by [name], [name], and study staff. Any staff members who leave the study for any reason will have access to study resources, including data, removed immediately.

Audio recordings of therapy sessions and check-in calls will be made via Duke Zoom or WebEx. We will record directly to a Duke-owned laptop, and then transfer recordings to the Duke shared server. In the event that we move back to in-person visits post-pandemic, we will use a Duke-owned iPhone or iPad that is encrypted at levels compliant with FIPS 140-2 standards. The device to be used will be hardened such that only the recording capability will remain. Recordings will be moved from the device to the Duke shared server (file path above) as soon as possible after the recordings have been made, and will then be deleted from the mobile device. Any device that is not in use will be stored in a locked filing cabinet in the study coordinator's office. Recordings will remain on the Duke shared drive until they are reviewed for fidelity by [name]. The recordings will be copied to an encrypted hard drive for permanent storage, and the copies on the Duke shared drive will be deleted. The encrypted hard drive will be stored in a locked file cabinet in [name] lab space at Duke. Only the key personnel listed on the staff listing will have access to the encryption password and/or the hard drive.

C.7.5. Data and Safety Monitoring Plan

We believe that provision of treatment for insomnia should enhance rather than jeopardize health status, and potential serious adverse events (SAEs) for participants in this project are not expected. Regardless, we will minimize potential risk by carefully screening potential participants and following established laboratory procedures for physiological data acquisition and data safety monitoring. The individuals responsible for data safety and monitoring will be the PIs, the co-Investigators, and the study coordinator.

[name] will serve as the primary safety monitor for the proposed study. There will be several ongoing mechanisms for monitoring and reporting of adverse events (AEs), including serious adverse events (SAEs): 1) ongoing participant contact via study personnel; 2) a telephone number provided to participants to report concerns related to study participation; 3) weekly meetings between [name] and study personnel. In order to monitor possible adverse events, participants will be instructed to report any adverse effects of study participation as soon as possible to research staff; they will have contact information needed to report these problems to study personnel. The PI will meet at least weekly with study personnel to discuss participants' reactions to the intervention, proper delivery of the intervention, and any adverse events or unanticipated problems. Monthly meetings between the investigators and the study coordinator will allow for ongoing progress reports, including the number of participants currently involved in the study groups, attrition rates, and scheduled data collection from participants, as well as notification and review of any AEs. Safety monitoring for adverse events will be conducted in real time by [name] and/or study coordinator. The following information about adverse events will be collected: 1) the onset and resolution of the AE, 2) an

assessment of the severity or intensity, 3) an assessment of the relationship of the event to the study (definitely, probably, possibly or not related), and 4) action taken (e.g., none, referral to physician, start or increase concomitant medication). [name] will determine the severity of the event, will assign attribution to the event, and will monitor the event until its resolution.

Any adverse events (AEs) will be reported to the Duke University Medical Center (DUMC) Institutional Review Board (IRB) in accordance with the local Human Research Protection Program's Standards of Practice. These guidelines require immediate reporting of any SAEs that are potentially study related. All research projects conducted at DUMC are required to have yearly IRB review. Reports of non-serious AEs or unanticipated problems that may increase risk for study participants or others are required as part of the annual progress reports. Additionally, any changes to the project between review periods must be approved by the IRB prior to implementation. All communication with the DUMC IRB will occur using Duke's electronic IRB system (IRIS).

C.7.6. Plans for Responding to Psychiatric Emergencies. Given the nature of PTSD symptoms, it is not unexpected that participants will experience increased distress associated with the assessment procedures and diagnostic clinical interviews. Our extensive clinical and research experience suggest that there is no serious risk in these patients associated with assessment and interview procedures as proposed. Over the past several years, several hundred patients with PTSD have participated in our research team's clinical trials, and there have been only rare occurrences of serious adverse events (i.e., hospitalization only) due to PTSD symptom increases.

The Traumatic Stress and Health Research Laboratory (TSHRL) has established, IRB-approved standards of practice (SOP) for the evaluation of risk of suicide and homicide. All study staff members are trained in use of the psychiatric emergencies SOP by a Ph.D. or Masters' level clinician with years of experience in working with persons with PTSD. The SOP includes a thorough risk assessment including evaluation of risk factors and protective factors associated with both suicide and homicide. Also included in the policy are differential recommendations for action based on determinations of low, moderate, or high risk. Any staff member conducting an interview in which moderate or high risk is determined will contact a senior staff person with clinical expertise in risk assessment [including the PI, co-investigator(s), and/or DUMC's Emergency Room]. At several time points throughout the study, participants are reminded that they are asked to inform the study therapist, study coordinator, or study PI if they experience a psychiatric emergency such as homicidal or suicidal ideation. In addition, participants are provided the telephone number of study staff who they can call in the case of psychiatric emergencies, including an after-hours contact number.

C.7.7. Post-Study Referrals for Participants. It is not unexpected that participants in both conditions may complete the study with residual PTSD and/or major depressive disorder symptoms. Because participants complete the PTSD Checklist (PCL5) and the Beck Depression Inventory-II (BDI-II) at multiple time points, we will refer to these scores at the end of the study as a gauge of residual symptoms. We will provide referrals for continued treatment to anyone with a score of 38 or higher on the PCL5 and/or a BDI-II score of 20 or higher (i.e., moderate to severe depression range). Additionally, referrals will be provided to participants who self-report distress at symptoms of PTSD or depression

(regardless of measure scores) and wish to continue with another form of treatment. The TSHRL has developed patient educational materials regarding available resources, including portable resource cards for participants. Participant resources may include local community mental health centers, local private mental health providers, Duke Adult Psychiatry Clinic, Duke's Psychology Clinic, and other resources such as emergency clinics and substance abuse treatment centers. Where applicable and convenient to the participant, direct referral will be made in addition to providing resource cards.

C.7.8. Subject Reimbursement.

Reimbursement to participants will offset the costs in time, effort, and possible lost wages associated with commitment to the study. Participants are paid as indicated in Table 2. Participants who are eligible for treatment will not receive payment for study participation until completion of the post-treatment actigraphy monitoring and labs. At that time, they will be paid \$700. If participants are excluded prior to randomization, or withdraw from CBT-I, they will be paid for their study participation to date.

Participants will be provided parking passes and/or bus passes to encourage attendance at all sessions.

Table 2. Participant Reimbursement

Task Completed	Payment
Screening Visit	Up to \$75
Sleep Apnea Screen and Actigraphy Monitoring	\$100
Baseline Labs (FMD, ABP)	\$225
Treatment Sessions (8)	\$0
Posttreatment Actigraphy Monitoring (1 week)	\$50
Posttreatment Labs (FMD, ABP)	\$250
Follow-up Actigraphy Monitoring (1 week)	\$50
Follow-up Labs (FMD, ABP)	\$250
Seed recruitment	\$60
TOTAL	\$1060

D. STATISTICAL ANALYSES

D.1. General Considerations and Descriptive Analyses

The study is designed as a two-arm trial to examine the effects of CBT-I on objective sleep parameters and CVD risk biomarkers. Statistical analyses will be performed using SAS, version 9.4 (SAS Institute, Cary, NC) and Mplus, version 7 (Muthén & Muthén, 2012). The first step in the analysis will be to calculate descriptive statistics, including graphical displays, to summarize all study variables. We will construct individual and mean trajectory plots of the longitudinal outcome variables to understand their general trends from baseline to post-intervention and 6-month follow-up. In addition, we will explore the variability and correlation structure of the longitudinal outcome variables. We will stratify by trauma exposure (combat or non-combat) and objectively measured sleep duration (<6 hours or \geq 6 hours).

Each of the study hypotheses will be examined using data collected at baseline, immediately following the 8-week intervention phase (i.e., post-intervention), and again at 6-month follow-up. Given nesting of these multiple observations within each participant, multilevel modeling (MLM) will be used to examine each set of hypotheses. MLM is a technique for analyzing repeated observations of data across multiple individuals (Searle, Casella, & McCulloch, 1992). Unlike repeated-measures ANOVA,

MLM uses all available data and can handle data missing at random. MLM can also accommodate imbalanced data and unequal variances.

To manage the problem of random positive findings when making multiple comparisons within each hypothesis (i.e., random significant findings occurring due to multiple proposed analyses), we will correct alpha using the “false discovery rate approach” described by Glickman (Glickman, Rao, & Schultz, 2014). This methodology differentiates random findings from hypothesis-driven outcomes and is more powerful than Bonferroni-type alpha adjustments that control the false-positive rate (Benjamini, 2010; Glickman, Rao, & Schultz, 2014; Schafer & Olsen, 1988; Searle, Casella, & McCulloch, 1992; Simes, 1986). Specifically, alpha correction will be applied to Aims 1 and 2 but not to the Supplemental Aim, given that any exploratory hypothesis that is supported would require validation with further research.

D.2. Missing Data Considerations

